7.3.3 Subject Discontinuation Criteria

A subject may discontinue from the clinical trial at any time for any reason.

It is the right and the duty of the investigator or sub-investigator to stop treatment in any case in which emerging effects are of unacceptable risk to the individual subject. In addition, the investigator or sub-investigator is to stop treatment of any subject with unmanageable factors that may interfere significantly with the trial procedures and/or the interpretation of results.

In this trial, a subject may discontinue from treatment, but continue to participate in the regularly scheduled activities as long as the subject does not withdraw consent. Discontinuation from treatment is “permanent”: once a subject is discontinued treatment, even though he/she continues to be monitored in the trial, he/she shall not be allowed to begin treatment again.

At a minimum collect the following information when a subject discontinues:

1. The reason the subject discontinued;
2. The date of the last dose of test products from the trial;
3. The date of the last assessment and/or contact. A follow-up contact (telephone or visit) will be arranged as appropriate;
4. (Serious) Adverse events;
5. Compliance with the test product administration as specified in this protocol;
6. Final Assessments:

Every effort should be made to ensure that all procedures and evaluations scheduled for the final trial visit are performed ([Section 2.2](#), Trial Flow Chart);

7. Retrieve all investigative products and test articles from the subject.

A subject must be discontinued from treatment for any of the following reasons:

1. The subject or legal representative (such as a parent or legal guardian) withdraws consent;
2. Adverse event criteria as specified in [Section 7.7.2.3.1](#).
3. Request of the subject (subjects have the right to discontinue treatment at any time for any reason);

4. Pregnancy;
5. Subjects with a prolonged QTc interval on a manual measurement of their post baseline ECG: greater than 500 msec. Study drug should be interrupted while evaluation and treatment of other etiologies is ongoing, and restarted within 5 days if QTc is within normal limits (less than or equal to 500 msec);
6. Subjects that develop clinically indicated visual problems (Grade 3 and/or Grade 4);
7. Subjects that develop an exfoliative cutaneous reaction, develops a skin lesion consistent with squamous cell carcinoma or melanoma.
8. Subjects who, during the course of the study, it is determined that they have a mold fungal infection caused by an organism that may be insufficiently covered by the current study therapy, or some other infection that requires combination antifungal therapy. Subjects who develop candidemia on study therapy may receive an echinocandin agent in addition to study therapy for a maximum duration of 14 days. A subject who needs a longer duration than 14 days of echinocandin therapy should discontinue study therapy.

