7.7.2.6.2 Temporary Interruption of Treatment for a Subject

Subjects who become temporarily unable to tolerate oral drug will be temporarily discontinued from the oral study medication and the IV medication should be substituted as provided in [Section 7.4.1.3.2](#). Additionally, if the subject cannot have IV therapy administered, the subject can take oral study therapy.

When the subject is again able to tolerate oral medication, the oral study drug should be administered.

Low dose cyclophosphamide use is allowed during the treatment period with a temporary interruption of study therapy on the day of cyclophosphamide dosing.

Temporary interruption may be required due to adverse events as described in [Section 7.7.2.3.1](#). A temporary interruption of no more than 3 sequential days without study medication will be allowed with resumption of treatment.

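### Section 7.3.3 item 5 lists QTc above 500 msec among mandatory discontinuations yet directs interruption and restart within 5 days, while Section 7.7.2.6.2 limits interruptions to 3 days, and no text says which governs

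*Combined protocol and SAP*

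**What the plan says.** Three places in the protocol deal with an on-treatment QTc above 500 msec or with the length of an interruption.

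- **Section 7.3.3 (Subject Discontinuation Criteria).** The section describes discontinuation from treatment as permanent: once it has happened, "he/she shall not be allowed to begin treatment again". It then opens a list with "A subject must be discontinued from treatment for any of the following reasons". Item 5 of that list is "Subjects with a prolonged QTc interval on a manual measurement of their post baseline ECG: greater than 500 msec". The same item continues: "Study drug should be interrupted while evaluation and treatment of other etiologies is ongoing", and drug is then to be "restarted within 5 days if QTc is within normal limits", which the item defines as 500 msec or less.
- **Section 7.7.2.6.2 (Temporary Interruption).** After stating "Temporary interruption may be required due to adverse events as described in" Section 7.7.2.3.1, it says: "A temporary interruption of no more than 3 sequential days without study medication will be allowed with resumption of treatment".
- **Section 7.6 item 12 (ECG).** For a QTc above 500 msec during treatment it asks for an assessment of possible causes. It mentions neither interruption nor discontinuation.

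Section 7.7.2.6.1 sends the reader back to Section 7.3.3 for the criteria that require discontinuation. No section says which of these texts takes precedence.

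**The concern.** A site that sees a QTc above 500 msec must decide whether the subject is interrupted or discontinued and, if interrupted, how long the gap may last. The heading over item 5 points to discontinuation, and the text of item 5 points to interruption. The two day limits, 5 and 3, sit in different sections without a cross-reference between them.

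The first thing at stake is that the same cardiac finding is handled in the same way at up to 155 centers. The analysis is touched in three secondary places: days on therapy (Section 8.11), percent compliance (Section 8.10), and the Tier 2 proportion of subjects who stop study therapy because of an adverse experience (Section 8.5.2). The situation is foreseeable, since the flow chart schedules post-baseline ECGs at Visit 3 and Week 1 and allows unscheduled ones.

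**Working it through.** The plan gives no figure to reproduce. The check sets the rules side by side for a subject with QTc above 500 msec whose value later falls to 500 msec or less. I count both limits as days off study drug from the start of the interruption. The documents do not define the starting point, so that is an assumption.

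| Days off drug at recovery | Section 7.3.3 item 5, own text | Section 7.7.2.6.2, read as general |
|---|---|---|
| Up to 3 | Restart | Resumption allowed |
| More than 3, up to 5 | Restart | Resumption not allowed |
| More than 5, or no recovery | No restart provided for; the item does not say what follows | Resumption not allowed |

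**Step 1, the day limits.** The two sections agree for gaps of up to 3 days. They give opposite instructions for gaps of more than 3 and up to 5 days, a band 5 − 3 = 2 days wide. Beyond 5 days neither provides for a restart.

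**Step 2, interruption or discontinuation.** Item 5 is placed under the mandatory heading, but its own text describes an interruption. It contains no sentence that turns the interruption into a discontinuation, so the last row of the table can be completed only by inference from the heading. Item 8 of the same list shows that the protocol can write such a condition: an added echinocandin is allowed for at most 14 days, and a longer need leads to discontinuation of study therapy.

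**Step 3, what it does to one subject's data.** This is an illustration on stated assumptions. Planned treatment is 84 days. Suppose the finding is made on Day 8, the last day of the Week 1 window, after that day's dose, QTc recovers after 4 days off drug, and treatment is otherwise complete. Section 8.10 defines compliance as days on therapy divided by days that should be on therapy, times 100. I keep the denominator at the 84 planned days.

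- Item 5 applied: 84 − 4 = 80 days on therapy; 80/84 × 100 = 95.2%. The subject is not a discontinuation.
- Section 7.7.2.6.2 applied: 8 days on therapy; 8/84 × 100 = 9.5%. The subject may count once in the Tier 2 discontinuation category.

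**Step 4, how many subjects.** The documents give no rate of on-treatment QTc above 500 msec and no distribution of recovery times, so the number in the 2-day band cannot be computed.

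**The case against.** A reader might infer that the protocol orders a permanent stop for every QTc above 500 msec and therefore contains a rule that cannot be followed. The documents do not support that. Item 5 never uses the word permanent; that meaning arises only by joining the heading to the general statement earlier in the section. Elsewhere the protocol treats interrupting and discontinuing as different acts: the Grade 4 rule in Section 7.7.2.3.1 offers both and provides for reintroduction. Item 8 shows that entries in this list can carry conditional management. A reasonable reading of item 5 is to interrupt first and discontinue only if QTc does not recover. This part of the objection stands. It does not remove the gap, because item 5 does not state that condition and gives no point at which discontinuation follows.

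The second objection is that the 3-day limit comes directly after a sentence about adverse-event interruptions under Section 7.7.2.3.1, which has no QTc rule. The limit could then be confined to those events, leaving item 5 as the specific QTc limit. That reading is possible but not secure. The sentence is worded generally, and a QTc above 500 msec may itself be recorded as an adverse event.

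The third objection is that the consequences are small, and this is largely right. Section 8.4 defines ITT, FAS and APaT only, so violator status removes nobody from a planned analysis set. Section 8.5.2 calls the Tier 2 intervals descriptive. Subjects with QTc of 500 msec or more at screening or baseline are excluded, and few post-baseline ECGs are scheduled. The rule is the same in both blinded arms.

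**Conclusion.** The inconsistency is in the text and is limited in extent. Item 5 does not say whether or when its interruption becomes the discontinuation that its heading requires. For gaps of more than 3 and up to 5 days, item 5 allows restart while Section 7.7.2.6.2, read as it is worded, does not. The second statement assumes that the 3-day limit covers QTc interruptions, which the protocol neither says nor excludes.

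For a single subject the choice of section can move exposure from nearly complete to a few days. The number of such subjects is unknown. A reader might go on to infer a threat to the primary result or a bias between the arms. The documents do not support either. Under the flow chart, randomized and treated subjects are followed for mortality to Day 114 whether or not they stop therapy, so the primary analysis through Day 42 is not directly affected. Nothing in the documents suggests that the ambiguity would act differently by arm. The point should be corrected because it concerns a cardiac safety instruction and needs only a change of wording.

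**What to change.** Reconcile Section 7.3.3 (the permanence statement, the list heading and item 5) with Section 7.7.2.6.2, so that a single rule states:

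1. whether a post-baseline QTc above 500 msec is an interruption or a discontinuation;
2. if it can be both, when the first becomes the second, including what happens if QTc has not recovered by the end of the permitted gap;
3. which interruption limit applies to this event, and from what point the days are counted.

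Align Section 7.6 item 12 by adding a reference to that rule. Which rule and which limit to adopt is for the sponsor's clinical team, and this review takes no position on it.

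The cost is amendment wording and notice to sites. Sample size, analysis sets and statistical methods do not change.

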7.3.4 Replacement of Subjects

A subject who discontinues from the trial will not be replaced.

7.4 Treatments

7.4.1 Trial Treatments

7.4.1.1 Treatments Administered

Treatment should be started as close as possible to the date in which randomized treatment is assigned, preferably on the same day.

Upon acceptance into the study, once all of the inclusion and exclusion criteria are met, at Baseline/Day 1 subjects will be stratified into two strata; high risk or not high risk (see [Section 7.4.1.2](#) for details). Within each stratum, subjects will be randomly assigned to one of two possible treatment arms: POS or VOR for a total duration of therapy of 12 weeks. The planned duration of study therapy is 12 weeks (84 days) with a maximum allowable duration of up to 98 days. Subjects will be randomized to POS or VOR in a 1:1 ratio. [Table 3](#) provides an overview of the treatment arms.

Table 3 Overview of Active Study Drug Dosing by Treatment Arms

Treatment Arms	IV Therapy ^a	Oral Therapy
Arm 1- Posaconazole (POS)	POS IV: Day 1 ^b : 300 mg BID Day 2-84 ^c : 300 mg QD	POS oral: Day 1 ^b : 300 mg BID Day 2-84 ^c : 300 mg QD
Arm 2 – Voriconazole (VOR)	VOR IV: Day 1 ^b : 6 mg/kg per body weight administered BID Day 2-84 ^c : 4 mg/kg per body weight administered BID	VOR oral: Day 1 ^b : 300 mg BID Day 2-84 ^c : 200 mg BID

^a Most subjects begin IV study drug and then step down/transition to oral study drug. If clinically indicated, some subjects may begin study drug with oral therapy instead of IV therapy.

^b Day 1 refers to the first day of subject taking either IV or Oral therapy. Subjects will only take one formulation, either IV or oral at a time

^c The planned duration of study therapy is 12 weeks (84 days) with a maximum allowable duration of up to 98 days.

IV=intravenous; POS=posaconazole; VOR=voriconazole

The dosing regimens will be as follows:

Arm 1 POS:

POS IV loading dose, 300 mg IV BID on Day 1; followed by 300 mg POS IV QD beginning on Day 2; followed by POS tablet 300 mg QD to begin following transition from POS IV. Transition to oral therapy may occur when the subject is considered clinically stable and able to take oral medication. Most subjects will initiate IV therapy, and then transition to oral; however, some subject may initiate via the oral route if clinical indicated. Subjects taking oral therapy on Day 1 will receive POS tablet 300 mg BID as a loading dose; followed by POS tablet 300 mg QD.

Subjects randomized to Arm 1 POS will receive a placebo infusion of 5% dextrose in water once a day to make the total number of infusions per day (2) similar for both treatment arms. Subjects will also receive double-dummy capsules with appearance consistent with VOR capsules when transition to oral therapy.

Arm 2 VOR:

VOR IV loading dose, 6 mg/kg IV BID on Day 1; followed by 4 mg/kg VOR IV BID maintenance dose, beginning on Day 2; followed by oral VOR capsule 200 mg BID to begin following transition from VOR IV. Transition to oral therapy may occur when the subject is considered clinically stable and able to take oral medication. Most subjects will initiate IV therapy, and then transition to oral; however, some subject may initiate via the oral route if clinical indicated. Subjects taking oral therapy on Day 1 will receive VOR capsule 300 mg BID as a loading dose; followed by VOR capsule 200 mg BID.

Subjects randomized to Arm 2 VOR will also receive double-dummy tablets with appearance consistent with POS tablets when transition to oral therapy.

7.4.1.2 Method of Treatment Assignment, Randomization, and/or Stratification

Subjects will be stratified prior to treatment assignment by risk status for mortality and poor outcome. Randomized treatment assignment will be stratified as follows:

High Risk: Any one of the following are present at Baseline or in the patient's medical history:

- Allogeneic hematopoietic stem cell transplant (HSCT).
- Relapsed leukemia, undergoing salvage chemotherapy.
- Liver transplant recipients [12].

Not High Risk: Any other eligible subject (none of the high-risk criteria are present at Baseline or in the subject's medical history)

Within each stratum, subjects will be randomly assigned (in a 1:1 ratio) to receive either POS or VOR according to a computer-generated randomization schedule using the interactive voice response system (IVRS).

7.4.1.3 Selection and Timing of Dose for Each Subject

7.4.1.3.1 Selecting the Dose for Each Subject

The rationale for the selection of doses to be used in this trial is presented in [Section 5.3](#). Dosing for all of the subjects will be based on [Table 3](#). The VOR IV dose will be calculated based on the screening weight of the subject. Details of the calculations can be found in the Pharmacy Manual.

Most subjects will begin antifungal azole (VOR or POS) therapy via the IV route. Azole therapy will be switched from IV route to the oral route when the subject is considered clinically stable and able to take oral medication. If during the course of the study, the subject can no longer tolerate oral medication, the subject may be switched back to IV therapy. Subjects with worsening clinical symptoms may also be switched back to IV therapy as clinically indicated. Based upon product labeling, similar study drug exposures for a 300 mg dose have been noted for POS IV and POS tablet, while 4 mg/kg IV VOR dosing achieves exposures similar to a 300 mg oral maintenance dose of VOR. Please refer to VOR EU product circular for full details [32].

If clinically indicated, some subjects may initiate study therapy via the oral route: Day 1 dosing of oral therapy is: POS 300 mg BID or VOR 300 mg BID.

For subjects with mild to moderate hepatic cirrhosis (Child-Pugh score of A or B), the standard loading dose will be used, but the maintenance dose will be reduced. See [Appendix 4](#) for Child-Pugh Classification. Appropriate dosing modifications will be included in the trial design in a blinded fashion.

7.4.1.3.2 Determining the Timing of Dose Administration for Each Subject

7.4.1.3.2.1 Posaconazole

[Table 4](#) provides what subjects randomized to the POS arm will receive when on IV therapy.

Table 4 Summary of POS IV Therapy

	Day 1 Dose	Day 2-84 Dose	Day 2-84 Dose for subjects with hepatic impairment
Drug	POS 300 mg twice a day	POS 300 mg first dose, placebo infusion second dose	POS 300 mg first dose, placebo infusion second dose
Volume	200 mL	150 mL	150 mL
Infusion rate	100 mL/hr	100 mL/hr	100 mL/hr
Infusion Duration	2 hr	1.5 hr	1.5 hr

[Table 5](#) provides what subjects randomized to the POS arm will receive when on oral therapy.

Table 5 Summary of POS Tablet Therapy

	Daily Oral Dose 300mg QD ^a	Daily Oral Dose for subjects with hepatic impairment 300mg QD
First Dose	2 orange VOR capsule placebos 3 yellow POS tablets	1 orange VOR capsule placebos 3 yellow POS tablets
Second Dose	2 orange VOR capsule placebos	1 orange VOR capsule placebos

^a If the subject starts on Day 1 with POS Tablet, they will receive 300 mg BID. The first dose should be: 3 orange VOR capsule placebos, and 3 yellow POS tablets. The second dose should be: 3 orange VOR capsule placebos, and 3 yellow POS tablets.

7.4.1.3.2.1.1 POS IV Solution

Subjects will have their IV infusions begun at the same time each day and are not to be administered until after the collection of the specified blood samples ([Section 7.6](#)).

POS IV will be given every 12 hours on the first day, with infusions being not less than 10 hours or no more than 14 hours apart. The subsequent POS IV infusions will be administered once daily 24 hours (\pm 2 hours) apart, in order to control one

source of variability in drug levels. Subjects who are randomized to POS will also receive a placebo infusion of 5% dextrose in water to make the number of infusions per day (2) similar for both treatment arms. Subjects will receive an IV infusion (POS or placebo) every 12 hours.

If the dosing of study medication is delayed, the dose should be administered as soon as possible. If it is more than 6 hours since the missed dose, the missed dose should be skipped, and the next dose should be administered at the regularly scheduled time. Any missed doses should be properly documented in the subject's eCRF and source documentation. The infusions will be administered via a programmable pump. On Day 1 the infusions will run for approximately 2 hours. The infusions on the subsequent days will run for approximately 1.5 hours. If necessary, the IV infusions may be prepared up to 24 hours prior to administration and stored at 2°C to 8°C refrigerated. The IV infusions should return to room temperature prior to administration.

IV infusions should be administered via a peripherally inserted central catheter, or a dedicated lumen of a central venous catheter. No infusions of study drug should be given via a peripherally inserted peripheral catheter as the duration of infusion mandated in the study for IV study therapy differs for peripheral catheter administration as compared to central catheter administration. Dosing duration is 90 minutes. The dosing of study drug via peripheral venous administration may not occur due to the potential occurrence of thrombophlebitis when IV study drug is given via peripheral route. POS IV infusions will be prepared in 5% dextrose in water.

Subjects will receive the IV infusions at a hospital or clinic. No IV doses should be missed.

See the Unblinded Pharmacy Binder and Administrative Binder for detailed POS IV Solution preparation and administration procedures.

7.4.1.3.2.1.2 Posaconazole Tablet

POS tablet will be started on the day after completion of the IV therapy (within 12 hours of the placebo infusion matching VOR IV) and continue up to Week 12 post randomization. POS tablet will be administered as a 300 mg dose QD (three 100 mg tablets, once a day). Every attempt should be made to ensure that the subject takes study medication at approximately the same time every day. If the dosing of study medication is delayed, the dose should be taken as soon as possible. Any missed doses should be properly documented in the subject's eCRF and source documentation.

If clinically indicated, some subjects may initiate study therapy via the oral route. For these subjects POS tablet will be administered on Day 1 as a 300 mg dose BID (three 100 mg tablets, twice a day at approximately 12-hour intervals). After Day 1, the dose will be 300 mg QD (three 100 mg tablets, once a day).

If a subject vomits within 15 minutes of POS tablet administration, the dosing should be repeated as soon as possible, following appropriate antiemetic treatment. The adverse event, supportive treatments, and ability to subsequently dose study medication should be appropriately recorded in the subject's eCRF. If repeated vomiting occurs, the subject should switch to POS IV therapy.

Details of the patient's food intake surrounding each dose of POS tablet or dummy placebo tablet should be recorded relative to each dose of POS tablet. Specifically, food intake data to be recorded should include whether the subject had no food, a light meal, a moderate meal or a full meal within 2 hours before or within 1 hour after taking study drug.

The exact time of POS study drug taken prior to collection of the population PK sample, as well as the exact time the Population PK sample blood draw occurs will be recorded in the appropriate eCRF.

7.4.1.3.2.2 Voriconazole

Table 6 provides what subjects randomized to the VOR arm will receive when on IV therapy.

Table 6 Summary of VOR IV Therapy

	Day 1 Dose	Day 2-84 Dose	Day 2-84 Dose for subjects with hepatic impairment^a
Drug	VOR 6 mg/kg twice a day	VOR 4 mg/kg twice a day	VOR 2 mg/kg twice a day
Volume	200 mL	150 mL	150 mL
Infusion rate	100 mL/hr	100 mL/hr	100 mL/hr
Infusion Duration	2 hr	1.5 hr	1.5 hr

^a The maintenance dose of VOR should be reduced for subjects with mild to moderate hepatic impairment (Child-Pugh Class A and B).

Table 7 provides what subjects randomized to the VOR arm will receive when on oral therapy.

Table 7 Summary of VOR Capsule Therapy

	Daily Oral Dose 200mg BID^a	Daily Oral Dose for subjects with hepatic impairment^b 100mg BID
First Dose	2 orange VOR capsules 3 yellow POS tablet placebos	1 orange VOR capsules 3 yellow POS tablet placebos
Second Dose	2 orange VOR capsules	1 orange VOR capsules

^a If the subject starts on Day 1 with VOR Solid Oral, they will receive 300 mg BID. The first dose should be: 3 orange VOR capsules, and 3 yellow POS tablet placebos. The second dose should be: 3 orange VOR capsules, and 3 yellow POS tablet placebos.

^b The maintenance dose of VOR should be reduced for subjects with mild to moderate hepatic impairment (Child-Pugh Class A and B).

7.4.1.3.2.2.1 Voriconazole IV

Subjects will have their IV infusions begun at the same time each day and are not to be administered until after the collection of the specified blood samples (Section 7.6).

VOR IV infusions must be given every 12 hours with no dose given less than 10 hours or no more than 14 hours apart. If the dosing of study medication is delayed, the dose should be administered as soon as possible. If it is more than 6 hours since the missed dose, the missed dose should be skipped, and the next dose should be administered at the regularly scheduled time. Any missed doses should be properly documented in the subject's eCRF and source documentation. The infusions will be administered via a programmable pump. On Day 1 the infusions will run for approximately 2 hours. The infusions on the subsequent days will run for approximately 1.5 hours. If necessary, the IV infusions may be prepared up to 24 hours prior to administration and stored at 2°C to 8°C refrigerated. The IV infusions should return to room temperature prior to administration.

IV infusions should be administered via a peripherally inserted central catheter, or a dedicated lumen of a central venous catheter. VOR IV infusions will be prepared in 5% dextrose in water.

Subjects will receive the IV infusions at a hospital or clinic. No IV doses should be missed.

See the Unblinded Pharmacy Binder and Administrative Binder for detailed VOR IV preparation and administration procedures.

7.4.1.3.2.2 Voriconazole Capsule

VOR oral capsule will be started on the day after completion of the IV therapy (within 12 hours of the last dose of IV VOR) and continued up to Week 12 post randomization. VOR will be administered as a 200-mg dose BID (two 100-mg capsules, twice a day at approximately 12-hour intervals). VOR oral capsules **SHOULD NOT BE TAKEN WITH A MEAL** and should be taken at least one hour before or one hour following a meal. If the dosing of study medication is delayed, the dose should be taken as soon as possible at least one hour before or one hour following a meal. Any missed doses should be properly documented in the subject's eCRF and source documentation.

If clinically indicated, some subjects may initiate study therapy via the oral route. For these subjects VOR oral capsule will be administered on Day 1 as a 300-mg dose BID (three 100 mg capsules, twice a day at approximately 12-hour intervals). After Day 1, the dose will be 200 mg BID (two 100-mg capsules, twice a day at approximately 12-hour intervals).

If a subject vomits within 15 minutes of VOR capsule administration, the dosing should be repeated as soon as possible, following appropriate antiemetic treatment. The adverse event, supportive treatments, and ability to subsequently dose study medication should be appropriately recorded in the subject's eCRF. If repeated vomiting occurs, the subject should switch to VOR IV therapy.

